1. PURPOSE OF THIS SURVEILLANCE

This post-marketing surveillance (hereinafter referred to as “the PMS”) is to be conducted for a medical device prescribed in Paragraph 1 in Article 14 of the Pharmaceutical Affairs Law (Law No. 145, August 10, 1960, hereinafter referred to as “PAL”) by a marketing approval holder or restrictive foreign approval holder of medical device prescribed in the standard for post-marketing surveillance and post-marketing study (excluding those set forth in Ministerial Ordinance Concerning the Standards for Executing Clinical Tests on Medical Devices, Ministerial Ordinance No. 36, March 23, 2005), which is part of the standard established by the Minister of Health, Welfare and Labor set forth in Paragraph 4 in Article 14-4 and Paragraph 4 in Article 14-6 (including when applied mutatis mutandis to Paragraph 4 in Article 19 of PAL). The objectives of the PMS are to observe the frequency, type, and degree of device deficiency to assure the safety of the new medical device as well as to collect information on evaluation of the efficacy and safety for reevaluation.

The PMS is to be conducted in accordance with Ministerial Ordinance Concerning the Standards for Post-marketing Surveillance and Tests of Medical Devices (Ministerial Ordinance No. 36, March 23, 2005, hereinafter referred to as “Good Post-marketing Study Practice: GPSP”).

2. ELIGIBILITY AND PLANNED REGISTRATION

2.1 Target Patient Population

Based on GPSP regulation, general patient population with ischemic heart disease who are eligible for treatment with XIENCE PRIME SV Everolimus Eluting Stent (Approval Number: 22500BZX00070000; Approval Date: March 7, 2013) , will be registered, with no particular inclusion/exclusion criteria, and may be eligible for angiographic follow-up at eight months and clinical follow-up at one year.

2.2 Enrollment Method

- Patient informed consent is required for registration of this PMS In cases where patient informed consent (or providing some type of information) is required for PMS per the participating site policy, the Sponsor will cooperate as needed.
- If it is known at the time of index procedure that the patient is not able to return for the 8-month follow-up visit for angiogram and for the 1-year clinical follow-up, then the patient should not be registered in the PMS.
- Patients who are treated (stent delivery system inserted into the body) by XIENCE PRIME SV will be registered (including provisional stenting for side branch treatment but excluding bail-out only use)
 - The observations will be compiled on a per-patient basis even if multiple stents are implanted during the index procedure.

- A patient whose side-branch is treated by XIENCE PRIME SV can be registered. In such a case, main vessel should be treated by XIENCE PRIME.
- A patient who are treated by other DES for planned stent and XIENCE PRIME SV for bail-out purpose cannot be registered.
- Additional revascularization procedures as a part of AE treatment and planned staged procedures will not be considered as another registration, or adverse events.
- A patient who is treated, but failed to be implanted by XIENCE PRIME SV and finally treated by other devices only (No XIENCE PRIME SV are implanted) must also be registered. In such a case, only the stent information, device deficiency information and reportable adverse events related to the PRIME stent, if any, are required to be captured. Follow-up of the patient who does not receive any XIENCE PRIME SV stent is not required.
- A patient may have another lesion(s) that may be treated by larger diameter stent(s). In such a case, treatment by XIENCE PRIME is preferable. Lesion(s) treated by other than XIENCE PRIME is not considered as the target lesion.

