2.3 Number of Patients to be Registered

The goal is to register 300 patients from approximately 30 sites.

MACE (composite of cardiac death, myocardial infarction and ischemia-driven target lesion revascularization) rate of this surveillance is expected to be 15%, based on past trials. For 300 patients, half of 95% confidence interval of MACE rate of 15% is 4.2%. This is 28% of expected MACE rate of 15%. This range will be enough to evaluate safety and efficacy of XIENCE PRIME SV in real world practice in Japanese hospitals.

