5.9 Adverse Event (Reportable Event)

Record the following adverse events (including procedural complications) and their details.

- All Coronary artery related adverse events*
 - Ischemic symptoms, evidences, including test results
 - Diagnostic angiogram
 - Revascularization
- All serious adverse events**
- All events for which relationship to the PMS Device cannot be ruled out, and
- All other adverse events related to taking antiplatelet medication(s)

* Send images to the corelab if revascularization is done to the target vessel.

** Serious adverse event: death, life-threatening, hospitalization (initial or prolonged), disability or permanent damage, congenital anomaly/birth defect, other serious (investigator's judgment).

Evaluate and record relationship of the above adverse events to the Device, procedure, and antiplatelet therapy, as well as the outcome of each event. If the event is an SAE, record the criteria for considering the event as an SAE.

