7.2 Independent Review of Adverse Events

Objective review of adverse events (Stent Thrombosis, Cardiac Death, Myocardial Infarction, and TLR/TVR) will be conducted by a third party (medical professional) up to 3 years post index procedure. These events will be reviewed based on ARC definition. QCA results from angiographic core-lab will be provided to the reviewer as necessary.

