4.4. Adverse Events

4.4.1. Adverse events (composite endpoint)

For adverse events (composite endpoint), incidence rates will be calculated by product for each time of onset.

No	Time of onset
1	Procedural day + 3 days from procedure date
2	Procedural Day + Day 4 or later to discharge date
3	Observation day of the day after discharge to Month 8
4	Observation day of Month 8 to Observation day of Year 1
5	Observation day of 1 year to the following day of 2 years
6	Observation day of the following day of Year 2 to Observation day of Year 3
7	Observation day of Year 3 to Year 4
8	Observation day following the observation day of Year 4 to the observation day of Year 5
9	During hospitalization
10	Up to 8 months
11	Until one year
12	Until 2 years
13	Up to 3 years
14	Up to 4 years
15	Until the end of the survey
16	Entire post-procedure

Table 18. Adverse events (composite endpoint, by time of onset)

- Analysis set: Stent implantation cases (newly enrolled patients)

Items [] indicating Breakdown

No	Item name
1	Target Lesion Failure [TLR Based on Cardiac Death, Myocardial Infarction Associated with Target Vessels, and Ischemic Findings].
2	Death + myocardial infarction + revascularization [death, myocardial infarction, revascularization]
3	Target vessel failure [cardiac death, myocardial infarction, TLR based on ischemic findings, TVR (non-TLR) based on ischemic findings, TVR (TLR or TVR (non-TLR)) based on ischemic findings].
4	Major adverse cardiac events (cardiac death, total myocardial infarction, TLR based on ischemic findings)
5	Death or myocardial infarction
6	Cardiac death or myocardial infarction
7	Myocardial infarction related to cardiac death or target vessel

Determination of myocardial infarction is based on the WHO (SPIRIT III) definitions

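### Protocol 2.2 says revascularization done to treat an adverse event is not an adverse event, but 5.9, 7.2 and the SAP record, review and count it as one, so TLR/TVR may be reported unevenly, mainly at years 1 to 5

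*Protocol*

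**What the plan says.** Protocol 2.2 (Enrollment Method) contains the rule at issue: "Additional revascularization procedures as a part of AE treatment and planned staged procedures will not be considered as another registration, or adverse events". It covers two kinds of procedure, revascularization that treats an adverse event and planned staged procedures. It denies both of them two things, status as a new registration and status as an adverse event.

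Protocol 5.9 opens with "Record the following adverse events (including procedural complications) and their details". Its first category is "All Coronary artery related adverse events", and revascularization is a sub-item there, beside ischemic symptoms and diagnostic angiogram. A footnote to that category adds "Send images to the corelab if revascularization is done to the target vessel".

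Protocol 7.2 says "Objective review of adverse events (Stent Thrombosis, Cardiac Death, Myocardial Infarction, and TLR/TVR) will be conducted by a third party", up to 3 years after the index procedure.

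Protocol 2.3 bases the survey size on the "MACE (composite of cardiac death, myocardial infarction and ischemia-driven target lesion revascularization) rate", expected to be 15%. SAP 4.4.1 (Table 18) lists the same composite as an adverse-event endpoint: "Major adverse cardiac events (cardiac death, total myocardial infarction, TLR based on ischemic findings". TLR based on ischemic findings is also part of target lesion failure and target vessel failure in that table. SAP 4.4.2 (Table 19) tabulates TLR, TVR, non-TVR and total revascularization as adverse events. SAP 4.4.4 uses TLR based on ischemic findings as a Kaplan-Meier event.

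**The concern.** The 2.2 sentence treats two different things alike. A staged procedure planned at the index procedure is not an outcome. A repeat procedure for restenosis or recurrent ischemia is the kind of procedure that the SAP's TLR and TVR rows exist to count. A site that reads 2.2 as a reporting rule has a reason not to enter such a procedure as an event, while a site that reads 5.9 enters it. With about 30 sites and no statement of which section governs, reporting could differ between them.

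The error would run one way for the composites: a missed TLR can lower MACE, target lesion failure and target vessel failure but cannot raise them. The confidence interval does not reflect this kind of error. In the survival analysis, a patient with an unreported TLR would be handled as censored.

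There is a smaller problem in the other direction. The SAP does not say how planned staged procedures are handled. If sites record them, nothing keeps them out of total revascularization or of TLR not based on ischemic findings in Table 19. Definition 11 in SAP 2.1 also keeps any patient with a total revascularization in the analysis set at every time point, so the handling of these procedures affects the denominators of the interval-specific rates.

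**Working it through.** **1. The plan's own figure.** Inputs: n = 300 and a MACE rate of 15% (Protocol 2.3), two-sided 95% (SAP 1.3), Clopper-Pearson interval (SAP 3.2).

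- Expected MACE patients: 0.15 × 300 = 45.
- Lower limit: 2.5% quantile of Beta(45, 256) = 11.16%.
- Upper limit: 97.5% quantile of Beta(46, 255) = 19.55%.
- Half-width: (19.55 − 11.16)/2 = 4.20 points, and 4.20/15 = 28.0%.

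The stated 4.2% and 28% reproduce. The point is textual and changes neither figure.

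**2. The provisions side by side.**

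| Place | Status of unplanned revascularization |
|---|---|
| Protocol 2.2 | Not an adverse event when done as part of AE treatment |
| Protocol 5.9 | Listed within the coronary adverse events to record |
| Protocol 7.2 | TLR/TVR named among the adverse events to review |
| SAP 4.4.1 and 4.4.2 | TLR counted under adverse events, alone and in composites |

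No other text narrows 2.2 or says which section governs.

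**3. Where a procedure could be missed.**

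- *To 8 months.* Protocol 5.5 has its own revascularization item and a follow-up angiogram, which the core lab analyzes (7.1). A procedure can be found here whatever its AE status.
- *Years 1 to 5.* Protocol 5.6 lists contact method, contact date, reportable adverse events, antiplatelet changes and device deficiency. There is no revascularization item, so a procedure enters only through the reportable-event route.
- *Unscheduled visits.* Protocol 5.7 asks for AE forms only when there is a reportable adverse event.
- *Core-lab images.* The instruction to send them is a footnote to the coronary adverse-event category in 5.9.
- *Independent review.* It stops at 3 years, while the SAP reports to 5 years. Nothing says that it searches for unreported procedures.

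The planning rate is a 1-year MACE (SAP 1.3), so for that figure the weaker capture applies to the interval from 8 months to 1 year. It applies throughout to the later rates.

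**4. Size.** Let *s* be the share of MACE patients whose only component is TLR, and *m* the share of those whose TLR goes unreported. Then

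observed MACE = 15% × (1 − *s* × *m*).

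Only TLR-only patients matter, because a patient who also has a myocardial infarction or cardiac death stays in MACE. The documents give neither *s* nor *m*, so the bias cannot be computed. The only firm scale is per patient: with 300 in the denominator, each one missed lowers the rate by 1/300 = 0.33 points.

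**The case against.** The strongest reply is that 2.2 belongs to the enrollment rules and speaks of revascularization that treats an adverse event, so an event already exists. On that reading the ischemic event is the AE, and the procedure is its treatment, neither a new registration nor a second AE. The underlying event is still reportable under 5.9 as coronary-related, and also as serious if it led to hospitalization. The nesting of revascularization beneath the coronary events in 5.9 fits this. The 8-month item, core-lab images and independent review are further routes by which a TLR can be found.

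Much of this stands. It disposes of two stronger readings that a reader might infer:

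- *That 2.2 takes TLR out of MACE.* It does not. Protocol 2.3 and SAP 4.4.1 define MACE by named components, ischemia-driven TLR among them, and nothing makes endpoint status depend on 2.2.
- *That a site following 2.2 would file nothing for a TLR.* The sentence removes AE status from the procedure, not from the event that it treats.

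The charitable reading does not remove the conflict, because the protocol does not state it. The sentence goes beyond registration to deny adverse-event status, and it puts unplanned procedures in one class with planned staged ones. Protocol 7.2 and the SAP tables treat TLR/TVR themselves as adverse events, not merely as details of another event. The alternative capture routes are also weakest after 8 months.

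It is also fair to say that MACE is not among the important evaluation items in Protocol 6.1, which are stent thrombosis and adverse events caused by antiplatelet medication. MACE is, however, the endpoint on which the survey was sized.

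**Conclusion.** The contradiction between Protocol 2.2 and Protocol 5.9, 7.2 and SAP Tables 18 and 19 is real and unresolved in the text. The supportable consequence is a risk of inconsistent TLR/TVR reporting between sites, mainly at the 1-to-5-year follow-ups. Any resulting bias in MACE, target lesion failure and target vessel failure would be downward.

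This rests on one assumption, that some sites would take 2.2 as a reporting rule; the documents neither confirm nor exclude it. A percentage loss of MACE should not be attached to this point. It would need a TLR-only share and a rate of non-reporting, neither of which is given, and it would have to assume that every other capture route failed. The MACE definition and the stated precision of 4.2% are unaffected.

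**What to change.** Reconcile the protocol sections and add one matching SAP rule.

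- **Protocol 2.2:** limit the exclusion from adverse events to staged procedures planned and documented at the index procedure. State that any other revascularization is not a new registration, but is recorded under 5.9 and classified as TLR, TVR or non-TVR.
- **SAP:** state that planned staged procedures are not counted in TLR, TVR or total revascularization, and do not trigger the event rule in definition 11 of SAP 2.1.
- **Sites:** send a short clarification, stressing that at the annual follow-ups an unplanned revascularization is to be entered as a reportable event.

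The cost is a short rewording of one protocol rule, one SAP sentence and a site notice. No new data items are needed, and the sample size statement stays as it is.

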2.3 Number of Patients to be Registered

The goal is to register 300 patients from approximately 30 sites.

MACE (composite of cardiac death, myocardial infarction and ischemia-driven target lesion revascularization) rate of this surveillance is expected to be 15%, based on past trials. For 300 patients, half of 95% confidence interval of MACE rate of 15% is 4.2%. This is 28% of expected MACE rate of 15%. This range will be enough to evaluate safety and efficacy of XIENCE PRIME SV in real world practice in Japanese hospitals.

3. PMS DURATION

Duration of patient registration for the PMS will not be set, however the target is to complete registry by June 30th, 2014.

Annual reports will be submitted to PMDA every year. After the re-submission, data will continue to be collected until 5 year follow-up is complete for all patients.

Patient data from the following time points will be collected

- Baseline (before procedure)
- Procedure
- Post-Procedure through discharge
- 8 months follow-up (follow-up angiogram)
- 1 year post-procedure (site visit is recommended but telephone contact is allowed)
- 2 year post-procedure (site visit/telephone contact)
- 3 year post-procedure (site visit/telephone contact)
- 4 years post-procedure (site visit/telephone contact)

- 5 years post-procedure (site visit/telephone contact)

4. PATIENT TREATMENT

Patient treatment strategy should be determined by the physicians based on standard PCI procedure at each of the sites. Physicians should review the most updated IFU, and carefully consider contraindications, warnings, and precautions when considering patient treatment.

Although dual antiplatelet management is ultimately determined by physicians, enrolled patients will be encouraged to receive adjunctive antiplatelet therapy consisting of an indefinite duration of aspirin in addition to a required minimum of 12 months of thienopyridine (clopidogrel, ticlopidine, etc.). It is recommended that physicians review the requirements of the most recent thienopyridine IFU before treating patients.

5. OBSERVATION ITEMS AT EACH TIME POINT

5.1 Baseline Information

1) Patient Basic Information

- Index Procedure Date (Date of Registration)
- Birth year and month
- Implant of XIENCE PRIME STENT (Only basic information, non-implant stent form and device deficiency form must be completed in the case all PRIME stents are failed to implant)
- Gender
- Height
- Weight
- Admission and Discharge dates

2) Cardiac Status at the Index Procedure and Cardiac History

- Cardiac Status (Symptom of ischemia) at the Index Procedure
- History of Myocardial Infarction
- Previous CABG
- Previous PCI

3) Risk Factors

- Family History of Premature Coronary Artery Disease

Confidential and Proprietary

Do not distribute or reproduce without the prior written permission of Abbott Vascular Inc.

- Smoking History
- Hypertension
- Dyslipidemia
- Diabetic Mellitus
- Renal Disease
- History of Stroke
- History of Major Bleeding
- Unstable Arrhythmia
- Chronic Anticoagulant Therapy

4) Pre-Procedure ECG**5) Pre-Procedure Cardiac Enzyme and Creatinine**

- Cardiac Enzyme
 - CK
 - CK-MB (If MI is suspected then must be measured per site standard practice)
- Serum Creatinine

6) Pre-Procedure Antiplatelet

- Aspirin
- Clopidogrel
- Ticlopidine
- Other anti-platelet medications
-

5.2 Procedure Information**1) General Information**

- Physician Name
- Procedure Start Time (Insertion of Guide Catheter)
- Procedure End Time (Removal of Guide Catheter)
- Access Site
- Number of Diseased Vessels
- Number of Treated Lesions
 - Treated only by XIENCE PRIME (Target Lesion)
 - Treated by XIENCE PRIME and Other Stent (Target Lesion)
 - Treated only by other devices (Non-target Lesion)

- LVEF

2) Lesion Information

Angiographic corelab analysis data will be adopted when it is applicable.

- Lesion Number
- Target or Non-target Lesion
- AHS Lesion Segment Number
- Lesion Type (de novo or restenosis)
- Complex Lesion
- Thrombectomy
- Lesion Preparation (pre-dilatation)
- Post-dilatation
- Use of Bailout Stent
- Total Number of Stents Implanted
- Other concomitant device (including intravascular imaging modalities), if any
- Stent recross by intravascular imaging modalities
 - Type of imaging modalities

3) Bifurcated Lesion (If applicable)

- Side Branch AHA Segment
- Bifurcation Lesion Type
- Technique Used
- Kissing Balloon

4) Lesion Visual Assessment (Pre and Post Procedure)

Angiographic corelab analysis data will be adopted when it is applicable.

- Lesion Length
- Reference Vessel Diameter
- %DS
- TIMI Flow

5) Stent Information

- Stent information must be recorded per lesion
 - Length and Diameter

- Deployment Pressure
- Successful Deployment
- Deployed Vessel (main vessel or side branch)

5.3 Post Procedure Information

1) Post-Procedure ECG

2) Post-Procedure

- Cardiac Enzyme
 - CK
 - CK-MB (If MI is suspected then must be measured per site standard practice)

5.4 Post-Procedure (Maintenance) Antiplatelet

- Type
- Start Date
- Daily Dose
- Termination or Continuation

5.5 Eight Months Follow-up

1) General Information

- Contact Method
- Contact Date
- Reportable adverse event since the last follow-up
- Change or termination of antiplatelet therapy
- Device Deficiency
- Follow-up Angiogram
- Ischemic Symptoms
- Revascularization

2) Angiographic Information

Angiographic corelab analysis data will be adopted when it is applicable.

- Lesion Length (if restenosis exist)
- Reference Vessel Diameter

- %DS

5.6 1~5 Years Follow-up (Every Year)

- Contact Method
- Contact Date
- Reportable adverse event since the last follow-up
- Change or termination of antiplatelet therapy
- Device Deficiency

5.7 Unscheduled Visit (Reportable AE related)

Complete AE form(s) if a patient visits the hospital with reportable adverse event(s).

5.8 Device Deficiency

- Date of deficiency
- Type of deficiency
- Did the device deficiency result in an adverse event?
- Description of deficiency/comment
- Product details (lot, serial numbers, etc.)

5.9 Adverse Event (Reportable Event)

Record the following adverse events (including procedural complications) and their details.

- All Coronary artery related adverse events*
 - Ischemic symptoms, evidences, including test results
 - Diagnostic angiogram
 - Revascularization
- All serious adverse events**
- All events for which relationship to the PMS Device cannot be ruled out, and
- All other adverse events related to taking antiplatelet medication(s)

* Send images to the corelab if revascularization is done to the target vessel.

** Serious adverse event: death, life-threatening, hospitalization (initial or prolonged), disability or permanent damage, congenital anomaly/birth defect, other serious (investigator's judgment).

Evaluate and record relationship of the above adverse events to the Device, procedure, and antiplatelet therapy, as well as the outcome of each event. If the event is an SAE, record the criteria for considering the event as an SAE.

6. EVALUATION ITEMS

6.1 Important Evaluation Items

Important evaluation items in this PMS are;

- 1) Stent Thrombosis
- 2) Adverse events caused by Anti-platelet Medications

6.2 Other Evaluation Items

Other evaluation items will be per standard drug eluting studies.

7. DATA ANALYSIS

7.1 Angiographic Core-Lab

Angiographic data at the index procedure and 8 months follow-up will be analyzed by Core-lab for lesion characteristics and coronary quantitative analysis.

